10.6 PSA Stabilization

PSA stabilization is referred to as any set of PSA values that do not meet the criteria for PSA response or PSA progression.

10.7 Time to PSA Progression

Time to PSA progression is defined as the interval between initiating treatment until the PSA rises 25% above nadir provided that the increase is at least 2 ng/mL.

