1.2 Secondary Objectives

- To assess the rate of PSA decline following fractionated ¹⁷⁷Lu-PSMA-617
- To assess radiographic response rate by RECIST 1.1 with PCWG3 modifications
- To assess biochemical and radiographic progression-free survival by PCWG3 criteria
- To assess overall survival following fractionated ¹⁷⁷Lu-PSMA-617
- To assess safety of fractionated ¹⁷⁷Lu-PSMA-617 as assessed by CTCAE 4.0
- To assess radiographic progression-free survival by PCWG3 criteria
- To assess changes in CTC count as measured by CellSearch and the rate of favorable CTC count and LDH at 12 weeks following fractionated ¹⁷⁷Lu-PSMA-617
- To examine whole body distribution of ¹⁷⁷Lu-PSMA-617
- Estimate radiation dosimetry of ¹⁷⁷Lu-PSMA-617 and correlate toxicity with radiation dosimetry

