6.1.2.2 Imaging visit (Day 8 ±1)

- Planar/SPECT imaging
- Targeted Physical Examination with vital signs and weight
- Medical History
- Brief Pain Inventory, FACT-P
- ECOG Performance Status
- CBC with differential and platelet count
- CMP (with direct bilirubin with known Gilbert's syndrome)
- Adverse event evaluation
- Concomitant medications

¹⁷⁷Lu-PSMA-617 infusion (Treatment Visit 2 Day 15 ±1 day)

The following procedures must be completed on the day of treatment with ¹⁷⁷Lu-PSMA-617:

- Targeted Physical Examination with vital signs and weight
- Medical History
- Brief Pain Inventory, FACT-P
- ECOG Performance Status
- CBC with differential and platelet count
- CMP (with direct bilirubin with known Gilbert's syndrome)
- PSA
- LDH
- Single intravenous dose of ¹⁷⁷Lu-PSMA-617 (Dose based on the Cohort in which the subject is enrolled)
- Adverse event evaluation
- Concomitant medications
- Concomitant procedures
- Optional imaging will be performed on consenting subjects between Treatment Visit 1 (Between D1-D4) and/or prior to Treatment Visit #2 on (D15 ± 1)

6.1.2.2 Follow-up visits: Follow up Visit 1 (Day 22 ±3), Follow up Visit 2 (Day 29 ±3), Follow up Visit 4 (Day 57 ±3)

- Targeted Physical Examination with vital signs and weight
- Medical History
- Brief Pain Inventory, FACT-P
- ECOG Performance Status
- CBC with differential and platelet count
- CMP (with direct bilirubin with known Gilbert's syndrome)
- PSA (Follow up Visits 2 & 4)
- LDH (Follow up Visits 2 & 4)
- Adverse event evaluation
- Concomitant medications

6.1.2.3 Follow-up lab visits: Follow up Visit 3 (Day 43 ±3); Follow up Visit 5 (Day 71 ±3)

- CBC with differential and platelet count
- CMP (with direct bilirubin with known Gilbert's syndrome)

These visits may be performed with any licensed provider at any CLIA certified lab, provided that the results are available/provided to the Investigator within allowable windows.

6.1.3. Scan (initial efficacy) Evaluation Visit (Day 85 ± 7); note that these study procedures are not expected to occur on a single day)

The following procedures must be completed during the initial scan visit(s):

- Targeted Physical Examination with vital signs and weight
- Medical History
- Brief Pain Inventory, FACT-P
- ECOG Performance Status
- CBC with differential and platelet count
- CMP (with direct bilirubin with known Gilbert's syndrome)
- PSA
- LDH
- Testosterone
- CTC count via CellSearch methodology
- CTC for research

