10.3 Duration of PSA response

Duration of PSA response is defined as the time from the first 25% PSA decline until the PSA value is confirmed to increase by 25% above the nadir, provided that the increase is at least 2 ng/mL above the nadir.

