10.5 PSA Progression

PSA progression will be defined as a rise of $> 25\%$ above either the pretreatment level or the nadir PSA level (whichever is lowest). PSA must increase by > 2 ng/ml to be considered progression. Confirmation requires a second consecutive rising PSA at least 2 weeks apart.

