Median bPFS, rPFS, and OS, including survival curves, will be estimated using Kaplan-Meier methodology. Greenwood's formula will be used to calculate 95% confidence intervals for the Kaplan-Meier estimates. Percent change in PSA from baseline will be described by mean/median and standard deviation/inter-quartile range, as appropriate, depending on the distribution of percent change from baseline. Modified RECIST response (i.e., CR, PR, and CR/PR proportions), CTC count response proportion, defined favorable LDH/CTC proportion, and associated 95% confidence intervals, will be estimated via binomial proportions.

All subjects will undergo baseline and subsequent ⁶⁸Ga-PSMA-HBED-CC PET/CT, and

those treated with ¹⁷⁷Lu-labeled products will undergo planar +/- SPECT imaging. We will analyze the data for associations with response to treatment as well as survival by chi-square tests/Fisher's exact tests and log-rank tests, respectively. For pre/post imaging comparisons, McNemar's chi-square test and paired t-tests/Wilcoxon signed-rank tests will be used, as appropriate. We plan to report data for each individual study as well as across the studies.

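### Section 10.7 times PSA progression from a rise with no stated confirmation, Section 10.5 requires confirmation, and no text says which rule sets the biochemical PFS event

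*Combined protocol and SAP*

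**What the plan says.** Three sections of the combined protocol and SAP use a 25% / 2 ng/mL PSA rule.

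- **10.3 Duration of PSA response** ends the response only when the rise is confirmed: "until the PSA value is confirmed to increase by 25% above the nadir".
- **10.5 PSA Progression** asks for a rise above 25% over the lower of the pretreatment and nadir values. It adds: "PSA must increase by > 2 ng/ml to be considered progression". It then states: "Confirmation requires a second consecutive rising PSA at least 2 weeks apart".
- **10.7 Time to PSA Progression** runs from the start of treatment "until the PSA rises 25% above nadir provided that the increase is at least 2 ng/mL". It does not mention confirmation and does not cite 10.5.

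Section 10.6 classes as stable any set of values that meets neither the response nor the progression criteria.

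The secondary objectives (1.2) include: "To assess biochemical and radiographic progression-free survival by PCWG3 criteria". The efficacy analysis at the end of 10.8 says: "Median bPFS, rPFS, and OS, including survival curves, will be estimated using Kaplan-Meier methodology". Neither place refers to 10.5 or 10.7.

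**The concern.** Section 10.7 is the only section that defines a time to PSA progression, and it is the one that leaves confirmation out. It restates the thresholds in full, and differently from 10.5, so it can be coded without looking at 10.5. A programmer who did so would count a single qualifying value as an event.

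A patient with one rise that then settles, and no qualifying response, would be stable under 10.5 and 10.6 but would have an event under 10.7. The two rules can give different event counts and dates for time to PSA progression, and for biochemical PFS if 10.7 supplies its event. Because the text does not choose, the choice could be made after the data are seen.

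**Working it through.** **Step 1. The rules side by side**

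| Element | 10.5 | 10.7 |
|---|---|---|
| Relative rise | more than 25% | 25% |
| Absolute rise | more than 2 ng/mL | at least 2 ng/mL |
| Reference value | lower of pretreatment and nadir | nadir |
| Confirmation | second consecutive rise, at least 2 weeks apart | none stated |

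The rules differ on all four elements. The first two matter only at exact equality.

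The reference value matters if nadir means the lowest post-treatment value. In a patient who never falls below baseline, 10.7 then has the higher threshold and may date progression later than 10.5. If nadir includes baseline, every confirmed 10.5 event also meets 10.7 on the same date or earlier, so 10.7 can only add events or bring them forward.

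**Step 2. Inputs for sizing**

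The plan states no figure to reproduce. Inputs:

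- PSA days 1, 15, 29, 57 and 85 (Table 8), then three visits 4 weeks apart (6.1.4): 85 + 28 = 113, 141 and 169.
- PSA level 44.9 ng/mL, the median in the earlier fractionated antibody study described in 2.5; 5 and 10 ng/mL also run.
- Within-patient CV: not in the documents. Assumed, 5% to 20%.
- True PSA flat, log-normal variation, running nadir that includes baseline.

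**Step 3. One pair of values**

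The log-scale SD is s = √ln(1 + CV²). The chance that one given later value exceeds one given earlier value by 25% is Φ(−ln 1.25 / (s√2)), with ln 1.25 = 0.223.

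- CV 5%: s√2 = 0.071, z = 3.16, chance 0.08%.
- CV 10%: s√2 = 0.141, z = 1.58, chance 5.7%.
- CV 15%: s√2 = 0.211, z = 1.06, chance 14.5%.

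Eight values give 8 × 7 / 2 = 28 later-versus-earlier pairs, and the nadir picks the lowest earlier value. The chance therefore builds up quickly over the schedule.

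**Step 4. Whole schedule**

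Simulation of 200,000 patients per setting, flat PSA of 44.9 ng/mL, at least one false progression by Day 169:

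| CV | One value (10.7 alone) | Confirmed: next value still above threshold | Confirmed: next value higher still |
|---|---|---|---|
| 5% | 1.8% | 0.1% | <0.1% |
| 7.5% | 27% | 4% | 2% |
| 10% | 59% | 17% | 11% |
| 15% | 88% | 46% | 32% |
| 20% | 96% | 63% | 47% |

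The two confirmed columns are two readings of 10.5. A rise on Day 169 cannot be confirmed within this window, which slightly favours the confirmed columns.

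The 2 ng/mL floor binds only when the nadir is below 2 / 0.25 = 8 ng/mL. Results at 10 ng/mL are therefore almost the same as at 44.9. At 5 ng/mL the one-value risk is 0%, 0.3%, 6%, 39% and 69% across the same CVs.

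**Step 5. A course that is not flat**

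Assume PSA halves by Day 85 and then doubles every 90 days, with confirmation meaning that the next value is also above threshold. At CV 10% the median is Day 141 under both rules. At CV 15% it is Day 113 for one value and Day 141 confirmed.

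**The case against.** The best defence is that 10.7 only dates an event that 10.5 has already defined. PSA progression is defined two sections earlier, with confirmation, and 10.6 relies on that definition. The objective also invokes PCWG3 criteria, and nothing ties biochemical PFS to 10.7. This stands in part: a reader might infer that the plan certainly scores random variation as progression, or that biochemical PFS has no definition except 10.7. The documents support neither. They leave two rules that conflict as written and do not say which applies. Naming PCWG3 does not settle which of the two in-protocol rules governs.

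A second objection is that the large percentages are a worst case. They need an assumed CV of 10-15% and an exactly flat PSA for six months. Yet eligibility requires progressive disease (3.2), and the phase II hypotheses put the proportion with a 30% decline at 35% or 60% (12.2). This stands. A reader might take 59-88% as the distortion of the trial's result, but Step 5 shows that the medians can coincide.

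A third objection is that confirmation is not always available. Short-term visits stop when new treatment starts (6.1.4), and 6.1.5 expects some patients to start it at PSA progression. This stands too, and the fix has to deal with it.

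**Conclusion.** The inconsistency is in the text and needs no assumption: 10.7 omits the confirmation that 10.5 and 10.3 require, and it also differs from 10.5 in its thresholds and reference value. If 10.7 is applied on its own, one unconfirmed rise could count as progression in a patient who is otherwise stable.

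The size rests on the unknown CV. In a flat-PSA patient near 45 ng/mL the excess is trivial at CV 5% (about 2% against under 1%) and large at CV 10% (59% against 11-17%). Confirmation reduces this error but does not remove it. The shift in the trial's own median cannot be derived from the documents.

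The effect is confined to a secondary, descriptive time-to-event summary. The DLT/MTD endpoint and the Simon test of 30% PSA decline do not use this rule.

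**What to change.** Reconcile 10.7 with 10.5:

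1. Define time to PSA progression as the time from first infusion to the first PSA that meets the 10.5 criteria, with the same thresholds and reference value, dated at that first rise once confirmed.
2. State that biochemical PFS uses this event or death, whichever comes first.
3. Say whether the confirming value must be higher than the first or only remain above the threshold, because the two readings differ (11% against 17% at CV 10%).
4. State how a last unconfirmed rise, or new therapy before confirmation, is handled. If such rises are censored, add a sensitivity analysis that counts them as events, because censoring them may be informative and lengthen the median.

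The cost is a few sentences and no extra visits, since PSA is already scheduled every 2 to 4 weeks. The visit windows allow Day 15 + 1 and Day 29 − 3, only 26 − 16 = 10 days apart, so in some patients the Day 57 value would have to confirm a Day 15 rise. The downside is that a few patients' last rises cannot be confirmed.

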10.8 Change in lesion size

In subjects with measurable disease, complete response (CR) is defined as complete disappearance of all measurable and evaluable lesions by physical examination or imaging studies and normalization of PSA with no appearance of new lesions for > 1 month. Partial response (PR) is defined as a 30% or greater reduction in the sum longest uni-dimensional diameter of all measurable lesions. There may be no new lesions. Stable Disease (SD) is characterized by subjects who do not meet the criteria of PR and who are without signs of progressive disease for at least 1 month. Disease Progression (DP) is defined as a greater than 20% increase in the sum longest uni-dimensional diameters of the indicator lesions or the appearance of new lesions. Bone scan progression (evaluable disease only) is requires at least 2 new lesions seen

on a scan subsequent to baseline followed by a repeat scan at least 6 weeks later with at least one new additional lesion.

Conventional Imaging studies (MRI, CT, Bone Scan) along with investigational images (⁶⁸Ga-PSMA-HBED-CCPET/CT imaging and ¹⁷⁷Lu-PSMA-617) will be performed during the study visits or as clinically indicated to assess disease response. In subjects enrolled in this study, the measurable disease response will be calculated using Response Evaluation Criteria in Solid Tumors (RECIST Version 1.1) with PCWG3 modifications.

Radiographic scans will be used to assess best overall response and radiographic progression based on modified RECIST criteria for soft-tissue lesions and protocol-specific criteria for bone lesions. Baseline images should be taken during Screening as close as possible to, and never more than 28 days before study visit 1. Every effort must be made to ensure the same radiographic method is used before and after treatment at scheduled visits. Radiographic progression free survival will be evaluated based on these results.

Analysis of Efficacy:

Median bPFS, rPFS, and OS, including survival curves, will be estimated using Kaplan-Meier methodology. Greenwood's formula will be used to calculate 95% confidence intervals for the Kaplan-Meier estimates. Percent change in PSA from baseline will be described by mean/median and standard deviation/inter-quartile range, as appropriate, depending on the distribution of percent change from baseline. Modified RECIST response (i.e., CR, PR, and CR/PR proportions), CTC count response proportion, defined favorable LDH/CTC proportion, and associated 95% confidence intervals, will be estimated via binomial proportions.

All subjects will undergo baseline and subsequent ⁶⁸Ga-PSMA-HBED-CC PET/CT, and

those treated with ¹⁷⁷Lu-labeled products will undergo planar +/- SPECT imaging. We will analyze the data for associations with response to treatment as well as survival by chi-square tests/Fisher's exact tests and log-rank tests, respectively. For pre/post imaging comparisons, McNemar's chi-square test and paired t-tests/Wilcoxon signed-rank tests will be used, as appropriate. We plan to report data for each individual study as well as across the studies.

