1.3 Exploratory Objectives

- Disease assessment with ⁶⁸Ga-PSMA-HBED-CC PET/CT prior to and following investigational treatment
- To assess genomic DNA repair pathways in relationship to outcome following fractionated dose ¹⁷⁷Lu-PSMA-617
- To assess patient reported outcomes using FACT-P and the Brief Pain Inventory short form
- To assess the immune effect of ¹⁷⁷Lu-PSMA-617
- To assess the reproducibility of ⁶⁸Ga-PSMA-HBED-CC PET/CT

2. BACKGROUND:

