Taken together, with >250 patients treated on these sequential clinical trials, we have

drawn the following conclusions: (i) there is a clear dose-response with more responses and longer survival at higher doses; (ii) there is clear dose-toxicity response in terms of myelosuppression (which is both predictable and reversible); (iii) dose-fractionation allows higher cumulative dose with comparatively less toxicity (including allowing concurrent chemotherapy); and (iv) without pre-selection for PSMA expression, approximately 90% have accurate tumor targeting, though the small minority with low/no PSMA expression by imaging have a lower likelihood of response. While ^{177}Lu -J591 mAb demonstrated significant efficacy, the major limitation in the optimization of therapeutic dose is the hematological toxicity (described in greater detail below).

With a single-dose, 70 mCi/m² of ^{177}Lu -J591 was the MTD, with dose-limiting myelosuppression in those receiving 75 mCi/m² (with 2 of 3 with dose-limiting hematologic toxicity).[Bander 2005] In the phase II study, this was confirmed with 70 mCi/m² of ^{177}Lu -J591 being tolerable with reversible myelosuppression, but with a significant amount of manageable grade 4 myelosuppression (including approximately 40% platelet transfusion).[Tagawa 2013]

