4. OVERVIEW OF STUDY DESIGN AND METHODOLOGY

4.1. Study Design

This is an open-label, single-center Phase I dose escalation trial designed to determine the cumulative MTD in a dose fractionation regimen in which ¹⁷⁷Lu-PSMA-617 will be given in 2 doses, 2 weeks apart. The dose escalation will start at 100 mCi (3.7 GBq) x 2 doses and escalate in increments of 50 mCi (1.85 GBq) for each dose to a maximum of 300 mCi (11.1 GBq) x 2 doses.

Patients must have documented progressive metastatic CRPC disease based on Prostate Cancer Working Group 3 (PCWG3) criteria in order to be eligible for enrollment. Upon meeting the inclusion and exclusion criteria and signing the informed consent and HIPPA form, subjects will undergo the screening. As part of the screening, subjects will get a single dose of ⁶⁸Ga-PSMA-HBED-CC and will have a PET/CT. Nuclear Medicine physician(s) will review the PET/CT scans to document PSMA expression at tumor site(s).

¹⁷⁷Lu-PSMA-617 dose fractionation regimen will be performed in patients with documented progressive metastatic CRPC. The ¹⁷⁷Lu dose (50 mCi – 300 mCi or 1.85 – 11.1 GBq) will be escalated in up to 6 different dose levels (3+3 at each dose level). Initially 3 subjects will be enrolled in Cohort 1 (100 mCi or 3.7 GBq x2 doses 2 weeks apart) and if any grade ≥ 3 toxicity is reported, then the next 3 subjects will be enrolled

in Cohort -1 (50 mCi or 1.85 GBq x2 doses 2 weeks apart) before proceeding to higher dose cohorts. Subjects will have Lutetium-177 Planar/SPECT Imaging on Day 8 (± 1 day) after the first dose of ^{177}Lu -PSMA-617. Optimal images will be performed on selected consenting subjects between initial treatment on D1 and D4 and prior to treatment #2 on D15. The enrollment ceiling of the dose escalation portion of the study is up to 46 study participants (six groups, with 3+3 subjects in each group). Each patient would receive 2 doses of the investigational agent, 2 weeks apart. The total dose received in 2 treatments will be **100 – 600 mCi (3.7 – 22.2 GBq)**.

Upon completion of investigational treatment with 2 doses of ^{177}Lu -PSMA-617, subjects will undergo ^{68}Ga -PSMA-HBED-CC injection and same day PET/CT at the end of study visit to document treatment response. Subsequently survival data and additional treatment(s) information will be captured from their routine Standard of care (SOC) visits.

Table 7: Treatment Plan with ^{177}Lu -PSMA-617

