9.2. Imaging Studies

Imaging studies (including ^{68}Ga -PSMA-HBED-CC PET/CT and ^{177}Lu -PSMA-617 Planar/SPECT Imaging) will be performed as described in schedule as well as clinically indicated to assess disease response. In subjects enrolled in this study, the measurable disease response will be calculated using Response Evaluation Criteria in Solid Tumors (RECIST Version 1.1) with PCWG3 modifications.

Consenting subjects will undergo an optional study involving two scans with ^{68}Ga -PSMA-HBED-CC (with a minimum of 6 h and maximum of 2 days between the two injections). This cohort of patients will be analyzed to ensure that the peak standardized uptake values (including SUV_{mean} , SUV_{max} , SUV_{peak} (SUV_{peak} not applicable to brain) of the lesions in the same patient/lesion is within an acceptable range of repeatability (+/- 30%) as demonstrated by prior radionuclide repeatability studies such as FDG and FLT.

10. MEASUREMENT OF EFFECT:

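### Imaging is tested against response and survival only with group-comparison tests, so any quantitative uptake measure would need an undefined cut point and would usually lose power

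*Combined protocol and SAP*

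**What the plan says.** Section 10.8, under Analysis of Efficacy, first describes baseline and follow-up ⁶⁸Ga-PSMA-HBED-CC PET/CT and post-treatment planar/SPECT imaging. It then says: "We will analyze the data for associations with response to treatment as well as survival by chi-square tests/Fisher's exact tests and log-rank tests". It names no imaging variable, grouping or cut point. No logistic, Cox, rank-sum or correlation method for this question appears elsewhere in the protocol.

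The following sentence reads: "For pre/post imaging comparisons, McNemar's chi-square test and paired t-tests/Wilcoxon signed-rank tests will be used, as appropriate". McNemar's test needs a categorical reading. The paired t and signed-rank tests need a quantitative or at least finely ordered one. The paragraph therefore expects both kinds of data.

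Section 9.2 lists SUVmean, SUVmax and SUVpeak for the same tracer, but only in the optional repeat-scan sub-study. Section 4.1 has nuclear medicine physicians review the screening scan to document PSMA expression, with no scale given. Section 1.3 lists the objective as exploratory: "Disease assessment with ⁶⁸Ga-PSMA-HBED-CC PET/CT prior to and following investigational treatment".

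**The concern.** The paragraph keeps the full measurement scale where it compares scans with each other and provides only group tests where it compares scans with outcome. If a quantitative measure such as SUV is carried into the second analysis as written, two things follow.

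- **Information is lost.** A patient just above the cut is treated like one far above it. Phase II has at most 27 patients, and footnote n to Table 8 lets patients enrol without PSMA imaging if tracer is unavailable, so there is little information to spare.
- **The cut is open.** With none defined in advance, it can be chosen after outcomes are known, which inflates false positives.

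The question matters to the programme. Of its antibody-based predecessor, section 2.5 says that "the small minority with low/no PSMA expression by imaging have a lower likelihood of response". Whether uptake of the present agent relates to benefit is a natural thing to learn from this trial, and a poorly matched test makes a real relation easier to miss.

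**Working it through.** **1. The plan's own power figure.** The only stated power is for the phase II PSA endpoint (section 12.2): continue if at least 7 of 16 respond, positive if at least 13 of 27 respond. With X ~ Bin(16, p) and Y ~ Bin(11, p),

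P(positive | p) = Σ over x = 7 to 16 of P(X = x) · P(Y ≥ 13 − x).

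This gives 0.098 at p = 0.35 and 0.900 at p = 0.60, matching the stated 0.10 and 0.90. None of it involves imaging.

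**2. Information kept by a cut.** For a normally distributed measure with a small graded effect, the large-sample efficiency of a cut with fraction f below it is φ(z_f)² / [f(1 − f)]. This needs no assumed effect size or significance level.

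| Split | φ(z_f) | Efficiency |
|---|---|---|
| 50/50 | 0.399 | 0.159 / 0.25 = 64% |
| 25/75 | 0.318 | 0.101 / 0.1875 = 54% |
| 10/90 | 0.175 | 0.0308 / 0.09 = 34% |

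A median split gives up about 36%, and 0.36 × 27 ≈ 10 patients' worth of information.

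**3. Power at the trial's sample sizes.** The documents give no effect size, significance level, event fraction or cut for this analysis, so these are assumptions: normal (log) uptake, two-sided 0.05, response 35% or 60% (the section 12.2 rates), odds ratio 2, 3 or 5 per SD, hazard ratio 1.5 to 2.5 per SD, and 70% or 100% events. Results are simulated.

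Points of power lost by a median split at n = 27:

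| Outcome | Full-scale test | Group test | Loss |
|---|---|---|---|
| Response | logistic | Fisher | 19–33 |
| Response | logistic | chi-square | 13–24 |
| Response | rank-sum | Fisher | 12–27 |
| Response | rank-sum | chi-square | 7–17 |
| Survival | Cox | log-rank | 13–23 |

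Two examples at n = 27:

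- Response 60%, odds ratio 3 per SD: Fisher 36%, chi-square 47%, rank-sum 62%, logistic 69%.
- Hazard ratio 2 per SD, 70% events: log-rank 55%, Cox 78%.

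At N = 63, the accrual ceiling, the median-split loss is 2 to 26 points for response and 0.5 to 21 for survival. The small values come with strong effects, where every test has high power.

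**4. How much is test size rather than cutting.** With no true effect at n = 27, rejection rates were about 3.2% for Fisher, 5.6–5.7% for chi-square, 4.3–5.0% for rank-sum and 5.5–6.2% for the logistic likelihood-ratio test. Part of the Fisher gap is therefore Fisher's conservatism. Rank-sum against chi-square (7–17 points) is the cleaner estimate of the cost of cutting.

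**5. When the true relation is a step.** Suppose at n = 27 the lowest fifth responds at 10% and the rest at 72%, with the cut exactly there. Power is then about 78% for Fisher, 84% for chi-square and only 40% for rank-sum. With a step at the median (35% v 85%) the figures are 71%, 78% and 64%. The ordering reverses, provided the right cut is known.

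**The case against.** The strongest reply is that the paragraph never names SUV. The predecessor antibody study scored planar imaging semi-quantitatively (section 2.5), and McNemar's test shows that categorical readings are expected here. For such readings chi-square, Fisher and log-rank are suitable. This stands. A reader might infer that the plan forces continuous uptake to be cut. The text does not say so; cutting follows only if a quantitative measure is carried into these tests. The paired t and signed-rank clause shows that such measures are expected, not that they enter the association analysis.

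A reader might also want one headline figure for the power loss. The documents support none: it depends on the effect, the cut, the tests compared and the sample size, and its sign depends on the shape of the relation.

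Nor does section 2.5 establish a 10/90 split for this trial. Its figure of about 90% accurate targeting concerns the J591 antibody, and the fractionated J591 study reports 79.6%. Neither describes PSMA-HBED-CC PET. The p = 0.07 from that study comes from an unstated test, so it cannot show a cost of grouping. The lesion SUVmax spread in section 2.3.1 comes from a diagnostic series in recurrent disease and is not a patient-level figure in mCRPC.

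Finally, the objective is exploratory, section 12.1 (written for phase 1) plans no formal testing, and section 12.5.2 makes imaging response descriptive. This limits the weight of the point, but section 10.8 still names specific tests, so they should suit the data.

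**Conclusion.** The point holds in conditional form and is a cheap improvement. The plan expects quantitative imaging measures, gives them no full-scale method for association with response or survival, and defines no cut. If such a measure is cut, it keeps about 64% of its information at best (median split, normal measure) and 34% at 10/90. At n = 27 with a median split, the power cost is about 7 to 33 points for response and 13 to 23 for survival.

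These ranges assume a graded, monotone relation, two-sided 0.05 and the effect sizes listed above, none of which the documents supply. The loss can fall to a few points or less at 63 patients with strong effects, and becomes a gain if a true threshold exists and is cut correctly. No stated power figure or decision rule in the trial is affected.

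**What to change.** In the Analysis of Efficacy text of section 10.8:

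- **Name the imaging variables**, for example baseline log SUV and the log ratio of Day 85 to baseline, and say how lesions are summarised to one value per patient.
- **Response:** use Wilcoxon rank-sum or logistic regression on the quantitative variable. Where dose cohorts are pooled, use logistic regression with dose level as a covariate, since the rank-sum test cannot adjust.
- **bPFS, rPFS and OS:** use Cox regression with the imaging variable as a continuous term, and dose level as a covariate where cohorts are pooled.
- **Day 85 change:** count time to event from the Day 85 scan, among patients still at risk then. Otherwise patients must survive to be scanned, and that time is wrongly credited to the change.
- **Categorical readings:** keep chi-square/Fisher and log-rank for visual or semi-quantitative scores and for Kaplan-Meier display, with any cut point fixed before outcomes are examined. If a threshold is thought likely, it can be pre-specified here.

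The cost is a few sentences of analysis wording, with no new patients, scans or visits. The small downside is that results are reported per unit of log SUV rather than as two groups; grouped curves can still be shown.
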